3.2 Rationale for study design, doses and control groups

This Clinical Study Protocol has been subjected to a peer review according to AstraZeneca standard procedures.

The objective of this study is to evaluate the effect of AZD6140 on the respiratory symptoms and physiological parameters that may be associated with the sensation of dyspnea in mild asthma and mild to moderate COPD patients with age range similar to that of the expected treatment population. Dyspnea was reported in association with AZD6140 administration in DISPERSE, a phase IIa study in outpatients with documented atherosclerosis, but not in healthy volunteers in the Phase I studies completed. The DISPERSE study assessed pharmacodynamic effects of AZD6140 at doses of 50 mg twice daily, 100 mg twice daily, 200 mg twice daily, and 400 mg once daily in the presence of acetyl salicylic acid (ASA) compared to clopidogrel plus ASA in subjects with documented atherosclerotic disease by evaluation of ADP-induced platelet aggregation and bleeding time. Two hundred subjects were enrolled with 163 exposed to AZD6140. Approximately 20% patients receiving AZD6140 reported dyspnea at the 400 mg dose level, with 5 patients in that group reporting dyspnea within the first 3 days of receiving an AZD6140 dose. Most reports were mild, self-limited, and resolved with continued dosing. There were no notable clinical findings (including bronchospasm) in patients experiencing dyspnea who had diagnostic evaluation of their symptoms. One patient reported symptoms of moderate intensity and discontinued the study. Of approximately 400 healthy volunteers that have received multiple doses of AZD6140 in Phase I studies, there has been only one report of dyspnea (unrelated to study drug).

Mechanistically, AZD6140 may affect the adenosine A3 receptor, and pre-clinical observations include increased respiratory rate in rats. The hypothesis of this observation is that AZD6140 may affect respiratory drive through adenosine receptors, with differing sensitivity to the sensation of dyspnea evoked by change in respiratory drive between healthy volunteers and patients.

Therefore, this study will assess the effect of AZD6140 on respiratory parameters, and will also provide tolerability data on the effect of AZD6140 in mild asthma and mild to moderate COPD patients.

This will be a double-blind, randomized, 2 cohort, placebo-controlled, 2-period crossover, pharmacokinetic/pharmacodynamic study. Mild asthma and mild to moderate COPD patients are included so that qualification of the differences in physiologic response and subjective experience of dyspnea can be extrapolated to the expected treatment population. The age range encompasses that of the Phase II study where dyspnea was first observed.

The primary variable will be respiratory rate and minute ventilation, based on the hypothesis of affecting adenosine receptors and preclinical observations. Cardiopulmonary cycle exercise testing is included because provocation of the system may elicit measurable changes in physiological parameters that are not otherwise observed. A sub-maximal protocol will be used for the exercise testing, and patients may terminate the test prior to experiencing dyspnea if they experience symptoms, which limit further exercising. Exercise testing also provides an opportunity to simulate the conditions and study the respiratory responses that could contribute to the sensation of dyspnea during daily activities.

A loading dose of 450 mg is chosen to maximize the potential of eliciting dyspnea. This dose will establish safety margins for a clinical loading dose that may be up to 270 mg. Dosing to 3 days will allow for attainment of steady-state plasma concentrations. Again, this will provide for assessment of dyspnea under clinically relevant conditions. A placebo crossover will be performed because dyspnea is a highly subjective sensation, and therefore comparison to a placebo baseline is desirable. In a healthy elderly volunteer study presently completing in the clinic this dose was well tolerated with no reports of dyspnea to date. This study will conclude the clinical phase prior to the start of the respiratory study in mid asthma and mild to moderate COPD patients.

Genetic polymorphisms may affect patients' responses to drugs. Genetic analysis on genes that may be involved in development of dyspnea associated with AZD6140 treatment will improve the understanding of the potential mechanism of this effect of AZD6140. Due to the limited number of patients in this study and low incidence of dyspnea associated with AZD6140 treatment, all patients participating in the study will be required to donate blood for genetic analysis.

A retrospective genetic analysis to explore the genetic variables in genes that are important to absorption and disposition of, and response to AZD6140 including dyspnea will be carried out. Genetic sampling will be mandatory to all patients enrolled. The genetic data from this study may be pooled with genetic results from other studies on AZD6140 to generate hypotheses to be tested in future studies.

3.3 Selection of study population

3.3.1 Study selection record

Investigator(s) must keep a record of patients who were considered for enrollment but never enrolled eg, patient screening log- according to local procedures. This information is necessary to establish that the patient population was selected without bias.

3.3.2 Inclusion criteria

For inclusion in the study patients must fulfill all of the following criteria:

- 1. Give written informed consent and agree to comply with all requirements of the study (this includes giving consent to donate blood for genetic testing);
- 2. Generally healthy male or female, who have mild asthma or mild to moderate COPD according to the following criteria:

Cohort	Volunteer Type	Age Range	Respiratory criteria
Α	Mild Asthmatic	35 –75 years (inclusive)	Clinical diagnosis > 1 year; $FEV_1 \ge 70\%$ predicted; no exacerbation in past 8 weeks; reversibility demonstrated within the past year (\ge 12% or 200 mL)
В	Mild to Moderate COPD	55 – 75 years (inclusive)	Clinical diagnosis > 1 year; $FEV_1 \ge 50\%$ predicted; no exacerbation in past 8 weeks; FEV_1/FVC ratio < 75%; history of tobacco smoking > 10 pack year

- 3. Females must be of non-childbearing potential defined as surgically sterile (hysterectomized, tubal ligation, or bilateral oopherectomy)or post-menopausal (cessation of regular menses for 12 months);
- 4. Weight at least 50 kg and have a BMI between 18 to 32 kg/m² inclusive. (BMI will be calculated as weight in kg/height in m² and will not be reported on the case report form.);
- 5. Have normal physical examination, laboratory values and vital signs; stable chronic medical conditions unless the investigator considers an abnormality to not be clinically significant or a symptom of mild asthma or mild to moderate COPD;
- 6. Patients are able to communicate with the investigator, and to understand and comply with all study requirements.

3.3.3 Exclusion criteria

Any of the following is regarded as a criterion for exclusion from the study:

- 1. History of hypersensitivity or adverse reaction to dicalcium phosphate and lactose excipients;
- 2. Use of leukotriene antagonists within 7 days of Day 1 of Period I;
- 3. Use of prescription medication for a chronic medical condition within 2 months of Study Day 1 of Period I (Appendix C identifies several accepted/unaccepted class of drugs); Use of long-acting inhaled corticosteroid medications for asthmatics is permitted in the study; Use of Atrovent inhaler for maintenance therapy of COPD is permitted;
- 4. Use of prescription medication for an acute medical condition within 4 weeks of Study Day 1 of Period I with the exception of maintenance inhalers;
- 5. Use of aspirin or any other drug known to increase the propensity for bleeding within 7 days of Study Day 1 of Period I;
- 6. Use of NSAIDs (ibuprofen) within 3 days prior of Study Day 1 of Period I;
- 7. Use of over-the counter preparations including herbal remedies such as Cordyceps sinensis, dan shen, feverfew, Ganoderma lucidum, ephedra, echinacea, St. John's Wort, and garlic, [aged extract taken on an ongoing basis], ginseng, ginkgo, and vitamin preparations within 7 days of Study Day 1 of Period I;
- 8. A history or presence of neurological, hematological, psychiatric, gastrointestinal, hepatic, or renal disease, or other condition known to interfere with the absorption, distribution, metabolism or excretion of drugs;
- 9. A personal history of any first, second or third degree heart block;
- 10. Screening ECG should not show any clinically significant abnormalities including significant AV block (2nd or 3rd degree heart block).
- 11. Any previous episodes of unexplained syncope;
- 12. A personal history of vascular abnormalities including aneurysms; a personal history of severe hemorrhage, hematemesis, melena, hemoptysis, severe epistaxis, or intracranial hemorrhage; rectal bleeding within 3 months prior to screening;
- 13. History suggestive of peptic ulcer disease or bleeding diatheses;
- 14. History of diabetes, claudication, CHF (congestive heart failure) or myocardial infarction in the past year;
- 15. History of anxiety disorder;

- 16. History of intubation/mechanical ventilation due to respiratory disease or bronchospasms;
- 17. Platelet count <100,000/mm³ at screening;
- 18. A significant history of alcohol or substance abuse within the past year;
- 19. Surgery or significant trauma within 3 months prior to Study Day 1 of Period I;
- 20. Unable to discontinue tobacco use during the inpatient stay of Periods I and II. At the investigator's discretion, use of nicotine supplement may be used for current smokers during the inpatient period;
- 21. Positive test results for HIV, (human immunodeficiency virus) HBsAg, (hepatitis B surface antigen) or hepatitis C antibody (anti-HCV);
- 22. Positive urine drug screen unless resulting from declared and confirmed medication;
- 23. Receipt of an investigational drug within 60 days prior to Study Day 1 of Period I;
- 24. Previous participation in an AstraZeneca AZD6140 study with the exception of a screening visit or those who now meet the new inclusion criteria based on this amendment.
- 25. Consumption of Seville oranges (e.g. orange marmalade) or grapefruit-containing products, alcohol, medicines or nutritional supplements within 1 week before Study Day 1 of Period I;
- 26. Consumption of caffeine-containing or methylxanthine products within 48 hours prior to Study Day 1 of each study period;
- 27. Blood donation within 90 days before Study Day 1 of Period I;
- 28. Clinical judgment by the investigator that the patient should not participate in the study;
- 29. A suspected/manifested infection according to WHO risk categories 2, 3 and 4 (Refer to Appendix D);
- 30. Involvement in the planning and conduct of the study (applies to both AstraZeneca staff or staff at the investigational site).

3.3.4 Restrictions

Patients will be required to adhere to the following restrictions:

1. No alcohol consumption will be allowed from 1 week prior to Study Day 1 of Period I, and through completion of the Follow-up Visit;

- 2. No consumption of caffeine-containing or methylxanthine products will be allowed within 48 hours prior to Study Day 1 of each study period through inpatient discharge on Day 5;
- 3. Seville oranges and grapefruit containing products will be restricted for 1 week prior to Study Day 1 of Period I, and through completion of the Follow-up Visit;
- 4. Patients will be required to refrain from strenuous physical exercise within 48 hours of Study Day 1 of Period I, and through completion of the Follow-up Visit with the exception of the study required cardiopulmonary exercise test on Study Day 4 of Period I and II;
- 5. Patients should refrain from over-the-counter preparations including herbal remedies such as Cordyceps sinensis, dan shen, feverfew, Ganoderma lucidum, ephedra, echinacea, St. John's Wort, and garlic, [aged extract taken on an ongoing basis], ginseng, ginkgo, and vitamin preparations within 7 days prior to Study Day 1 of Period I, and through completion of the Follow-up Visit unless approved by the investigator and sponsor;
- 6. Refrain from taking aspirin or any other drug known to increase the propensity for bleeding within 7 days prior to Study Day 1 of Period I, and through completion of the Follow-up Visit unless otherwise agreed to by the investigator and sponsor;
- 7. Refrain from taking NSAIDs (ibuprofen) within 3 days prior to Study Day 1 of Period I, and through completion of the Follow-up Visit unless otherwise agreed to by the investigator and sponsor;
- 8. Scheduled surgery, including dental surgery, at anytime following the screening visit, and through completion of the Follow-up Visit.
- 9. No use of tobacco or other nicotine-containing products from screening and throughout the Follow-up Visit. At the investigator's discretion, use of a nicotine supplement may be used for current smokers during the study period.

3.3.5 Discontinuation of patients from treatment or assessment

3.3.5.1 Criteria for discontinuation

Patients may be discontinued from study treatment and assessments at any time. Specific reasons for discontinuing a patient from this study are:

- Voluntary discontinuation by the patient, who are at any time free to discontinue their participation in the study without prejudice to further treatment
- Safety reasons as judged by the investigator and/or AstraZeneca including moderate to severe dyspnea that does not resolve or return to patient's baseline within 2 weeks.
- Severe non-compliance to protocol as judged by the investigator and/or AstraZeneca.

- Incorrect enrollment (ie, the patient does not meet the required inclusion/exclusion criteria) or randomization (ie, the patient is not allocated study drug as described in the protocol) of the patient.
- Patient lost to follow-up
- A suspected/manifested infection according to WHO risk categories 2, 3, and 4 (Refer to Appendix D).
- Non-exercising respiratory rate >25 per minute, heart rate >120 per minute or SaO_2 <85%; or FEV1 < 1 Liter; or Peak Expiratory flow < 80L/min; or negative change in Modified Borg Scale /Bidirectional Dyspnea scale >3 points on 2 successive assessments (exclude exercising). All these criteria should be at investigator's judgment in conjunction with clinical findings.

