Patients will be admitted to the study center on Day -1 and will reside in the study center from Study Day-1 until completion of all protocol-driven procedures and assessments on Study Day 5 of Period I. The assessments on Study Day -1 of Period I, will reconfirm the patient eligibility to participate in the study. The results of the assessments must be confirmed before the patient is randomized and receives study medication on Day 1 of Period I.

All patients will be required to begin an overnight fast on the evening of Study Day -1. On Study Day 1 of Period I, each patient will receive one of the following treatments according to the randomization schedule:

Treatment A: A single, oral dose of 450 mg AZD6140 (5 x 90 mg micronised tablets) will be administered in the AM of Study Day 1; followed by a single, oral dose of 180 mg AZD6140 (2 x 90 mg micronised tablet) in the PM (12 hours after the first dose); thereafter, 180 mg AZD6140 (2 x 90 mg micronised tablet) will be administered bid (every 12 hours) on Study Days 2 and 3 and in the AM only on Study Day 4.

Treatment B: A single, oral dose of AZD6140 matching placebo (5 placebo tablets) will be administered in the AM of Study Day 1; followed by a single, oral dose of AZD6140 matching placebo (2 placebo tablets) in the PM (12 hours after the first dose); thereafter, AZD6140

matching placebo (2 placebo tablets) will be administered bid (every 12 hours) on Study Days 2 and 3 and in the AM only on Study Day 4.

A blood sample for genetic analysis will be taken from patients on Study Day 1 prior to dose administration (Period I only). Blood samples for the determination of AZD6140, and its metabolite AR-C124910XX, in plasma will be collected on Study Days 1, 2, 3 and 4 in each treatment. Refer to Table 2, Table 3 and Sections 4.3 and 4.4 for the timing and detailed descriptions of all the study procedures and assessments to be performed in each treatment.

If a patient experiences a spontaneous dyspnea episode any time throughout the inpatient study period (beginning with first dose administration), specific study procedures need to be completed sequentially as described in Table 3. These procedures should be completed at the onset of each dyspnea episode with the exception of an occurrence during cycle exercise testing.

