4.3 Pharmacodynamic measurements

4.3.1 Modified Borg Scale

The modified Borg CR-10 scale will be used to assess the patient's perception of dyspnea at the times pre-specified in the study plan, as well as during the cycle exercise test. Numeric measurement will be recorded on the pCRF and the scale will be kept in the appropriate patient's source document files. (Refer to Appendix E.)

The patient should be given the following instructions:

"This is a scale for rating breathlessness. The number "0" represents no breathlessness. The number 10 represents the strongest or greatest breathlessness you have ever experienced. Prior to completing the minute ventilation test and spirometry tests, you will be asked to point to a number with your finger, which represents your perceived level of breathlessness at that time. Use the written description to the right of the number to help guide your selection. I will say the number

out loud in order to confirm your choice. If you have an even stronger or greater intensity of breathlessness than you have ever previously experienced, you should then point to the word "maximal" if the severity is greater than 10."

The patient should be given the following additional instructions during the cycle exercise test:

"Every 2 minutes during the exercise test you will be asked to complete this assessment. During the cycle exercise you may have an even stronger or greater intensity of breathlessness than you have ever previously experienced. You should then point to the word "maximal", if the severity is greater than 10. You can tell us this number after the mouthpiece has been removed."

The numeric value the patient reports should be recorded on the pCRF.

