4.3.2 Bidirectional Dyspnea Index

The Bidirectional Dyspnea Index is a category scale in which words describing varying degrees of ease or difficulty of breathing are linked to number (+5 to -5). Thus, patients categorize their sense of breathing effort during study time points as being unchanged (zero), slightly (-1), moderately (-2 to -3), or markedly (-4 to -5) easier; or slightly (+1), moderately (+2 to +3), or markedly (+4 to + 5) harder than during the immediately preceding period. (Refer to Appendix F.)

The numeric value the patient reports should be recorded on the pCRF.

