Appendix E Modified Borg Scale

Score		Sensation of breathlessness/dyspnea
0	=	Nothing At All
0.5	=	Very, very slight (just noticeable)
1	=	Very Slight
2	=	Slight
3	=	Moderate
4	=	Somewhat Severe
5	=	Severe
6	=	
7	=	Very severe
8	=	
9	=	Very, very severe (almost maximal)
10	=	Maximal

Modified Borg Scale

The subject should be given the following instructions:

"This is a scale for rating breathlessness. The number "0" represents no breathlessness. The number "10" represents the strongest or greatest breathlessness you have ever experienced. Prior to completing the minute ventilation test and spirometry tests, you will be asked to point to a number with your finger, which represents your perceived level of breathlessness at that time. Use the written description to the right of the number to help guide your selection. I will say the number out loud in order to confirm your choice. If you have an even stronger or greater intensity of breathlessness than you have ever previously experienced, you should then point to the word "maximal" if the severity is greater than 10."

The subject should be given the following additional instructions during the cycle exercise test:

"Every two minutes during the exercise test you will be asked to complete this assessment. During the cycle exercise you may have an even stronger or greater intensity of breathlessness than you have ever previously experienced. You should then point to the word "maximal", if the severity is greater than 10. You can tell us this number after the mouthpiece has been removed."

Clinical Study Protocol: Appendix FDrug SubstanceAZD6140Study CodeD5130C00034Appendix Edition Number1.0Appendix DateInterference

Appendix F Bidirectional Dyspnea Index Clinical Study Protocol: Appendix F Study Code D5130C00034 Appendix Edition Number 1.0 Appendix Date:

Sco	ore	Change in Breathlessness/Dyspnea
-5	=	Very marked improvement
-4	=	Marked improvement
-3	=	Moderate improvement
-2	=	Slight improvement
-1	=	Very slight improvement
0	=	No change
+1	=	Very slight worsening
+2	=	Slight worsening
+3	=	Moderate worsening
+4	=	Marked worsening
+5	=	Very marked worsening

Bidirectional Dyspnea Index

The subject should be given the following instructions:

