"This is a scale for rating changes in breathlessness. The number -5 represents a very marked improvement. The number +5 represents a very marked worsening. Prior to each set of three spirometry tests, you will be asked to point to a number with your finger, which represents your perceived level of breathlessness compared to how you felt prior to taking your most recent dose of medication. Use the written description to the right of the number to help guide your selection. I will say the number out loud in order to confirm your choice."

Clinical Study Protocol Appendix G				
Drug Substance	AZD6140			
Study Code	D5130C00034			
Appendix Edition Number	1.0			

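### The dyspnea-scale stopping criterion asks for a negative change, which is improvement on both named scales, and the Bidirectional Dyspnea Index has two different reference points

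*Combined protocol and SAP*

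**What the plan says.** The last bullet of section 3.3.5.1 lists limits for discontinuation: non-exercising respiratory rate above 25 per minute, heart rate above 120 per minute, SaO2 below 85%, FEV1 below 1 L, peak expiratory flow below 80 L/min, or a "negative change in Modified Borg Scale /Bidirectional Dyspnea scale >3 points on 2 successive assessments (exclude exercising"). It closes with "All these criteria should be at investigator's judgment in conjunction with clinical findings".

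The scales are defined elsewhere:

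- **Modified Borg Scale** (section 4.3.1, Appendix E): 0 is no breathlessness, and "The number 10 represents the strongest or greatest breathlessness you have ever experienced".
- **Bidirectional Dyspnea Index, direction** (Appendix F): "The number -5 represents a very marked improvement", and +5 is labelled "Very marked worsening". Section 4.3.2 agrees that negative is easier and positive is harder.
- **Bidirectional Dyspnea Index, reference point**: section 4.3.2 describes the top scores as "markedly (+4 to + 5) harder than during the immediately preceding period". Appendix F, to which 4.3.2 refers, has the patient rate the "perceived level of breathlessness compared to how you felt prior to taking your most recent dose of medication".

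Table 2 schedules both scales through each period. Table 3 adds them at every spontaneous dyspnea episode. Of the Table 3 procedures, section 3.1.2 says: "These procedures should be completed at the onset of each dyspnea episode with the exception of an occurrence during cycle exercise testing".

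**The concern.** There are two faults, the first more important than the second.

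**Direction.** A numerically negative change is an improvement on both scales. The only stopping criterion based on a symptom scale therefore points the wrong way as written, and no other section corrects it. On the Index, *negative* is also the printed sign of the improvement scores, so the word is easily taken literally.

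**Reference point.** At 3, 4 or 8 hours after a dose, the preceding period and the time before the last dose can be different comparisons. The same Index score can then mean different things. A rule that needs two successive high scores is sensitive to this, because a score relative to the previous assessment returns to 0 once the worsening has settled in.

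The rule is for patients with asthma or COPD who receive a 450 mg loading dose that section 3.2 says was chosen to make dyspnea more likely. A safety limit in that setting should state its direction.

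**Working it through.** The plan has no figure of its own to reproduce here. The check has two parts.

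**1. Which scores meet the clause**

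Inputs: the printed Borg scores (0, 0.5, 1, 2, ..., 10) and the Index scores (-5 to +5). The Index is already a rating of change, so its score is taken as the change. The clause does not say this.

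| Scale | As written: change below -3 | As very probably meant: change above +3 |
|---|---|---|
| Borg, baseline 0 or 0.5 | impossible | score of 4 or more |
| Borg, baseline 1 | impossible | 5 or more |
| Borg, baseline 2 | impossible | 6 or more |
| Borg, baseline 3 | impossible (3 - 0 = 3, not above 3) | 7 or more |
| Borg, baseline 4 | 0 or 0.5 | 8 or more |
| Index | -4 or -5 | +4 or +5 |

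No worsening on either scale meets the literal wording.

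**2. Effect of the reference point, with the direction corrected**

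Inputs from Table 2, in hours from the Day 1 morning dose:

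- Resting assessments: 0 (pre-dose), 2, 3, 4, 8, 12, 24, 27, 48, 51, 72, 74, 75, 76, 80, 84, 96. That is 17 times, 16 intervals and 96 h.
- Doses: 0, 12, 24, 36, 48, 60, 72.

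Assumptions:

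- A 4-point worsening starts inside an interval and persists.
- An assessment at a dose time is made before the dose.
- The Day 4 post-exercise assessment is not counted.
- Borg change is taken from that period's Day 1 pre-dose value. The clause names no reference; section 6.1.2 speaks only of baseline in each period.
- The preceding period in 4.3.2 is read as the previous assessment. The protocol does not define the word there.

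The test is a score above 3 on two successive assessments. The table gives the intervals in which every onset passes, with total passing onset hours in brackets.

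| Reference | Scheduled assessments only | With the Table 3 assessment at onset |
|---|---|---|
| Index, previous assessment (4.3.2 as read) | 0 of 16 | 0 of 16 |
| Index, before the most recent dose (Appendix F) | 9 of 16 (20 of 96 h) | 14 of 16 (78 of 96 h) |
| Borg, Day 1 pre-dose | 15 of 16 (84 of 96 h) | 16 of 16 (96 of 96 h) |

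- **Previous assessment:** the patient scores +4 at the first assessment and 0 at the next, so the rule is never met.
- **Appendix F, scheduled only:** it passes for onsets at 0-8 h and 72-84 h, and 8 + 12 = 20 h. Elsewhere a dose resets the reference before the second high score, or only one assessment remains.
- **Appendix F, with the onset assessment:** it fails only when a dose falls between onset and the next assessment. The 36 h dose affects onsets at 27-36 h and the 60 h dose affects onsets at 51-60 h. So 96 - 9 - 9 = 78 h, and 78/96 = 81%.
- **Borg:** on scheduled assessments alone it misses only the last interval (84-96 h), where one assessment remains: 96 - 12 = 84 h. The onset assessment closes that gap.

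**The case against.** The strongest reply on direction is that *negative* in ordinary clinical speech means for the worse. Every other limit in the bullet marks deterioration, the whole bullet is left to the investigator, and no investigator would withdraw a patient for breathing more easily. This stands as an account of intent and is why the harm is small. It does not make the wording sound, because a numeric limit on signed scales should give its sign.

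On the reference point, section 4.3.2 can be read as a general description that defers to Appendix F, whose script is what patients actually hear. The 0 of 16 result depends on the other reading. The slash between the scale names most naturally means either scale, and Borg then catches the worsening whichever Index reference is used. Both points stand. The inconsistency weakens the Index arm only, and only under that reading.

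The permanent 4-point step is stylised. The 81% is a share of onset hours, not a probability of detection.

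Other safeguards remain: the physiological limits, discontinuation at any time for safety reasons, the Table 3 assessments, albuterol as needed with investigator approval (section 3.4.5), and the expectation in section 3.1.2 that dyspnea should resolve or return to baseline before Period II.

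**Conclusion.** The concern holds and is minor. That the clause points to improvement on both scales follows directly from the printed definitions, taking the Index score itself as the change. That the two Index reference wordings differ is also plain from the text.

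The size of the second fault is conditional. It disables the Index arm completely if 4.3.2 means the previous assessment. Under the Appendix F reference, with the onset assessment, the arm works for 78 of 96 onset hours. In the intended direction the criterion as a whole still works, provided either scale suffices and Borg is measured from the Day 1 pre-dose value.

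No result is affected: section 6.4.3 plans no formal analysis, and nothing in the analysis uses this clause.

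**What to change.** In section 3.3.5.1, replace the clause with:

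> *an increase (worsening) of >3 points on the Modified Borg Scale from that period's Day 1 pre-dose value, or a Bidirectional Dyspnea Index score of +4 or +5, on 2 successive non-exercise assessments*

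Keep the sentence on investigator judgment. In section 4.3.2, change the Index reference to the time before the most recent dose, as Appendix F already tells patients. The Day 1 pre-dose Borg reference is a proposal, since the protocol names none; the sponsor may choose another but should state it.

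The cost is one sentence in 3.3.5.1, one phrase in 4.3.2 and a memo to the site. Assessments, analysis and sample size do not change.
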